8.8. Exploratory Efficacy Analyses

8.8.1. Magnetic Resonance Imaging

MRIs will be evaluated by a central reader. The following analyses of MRI will use the Efficacy Analysis Set. [REDACTED]

8.8.1.1. Liver Fat Content by MRI Proton Density Fat Fraction (PDFF)

[REDACTED] The PDFF metric is displayed as a median and interquartile range (IQR), the median will be used in all analyses.

Analyses of liver fat content (LFC) by MRI by MRI-PDFF will be based on the Efficacy Analysis Set. For the purposes of LFC analyses, absolute change is equivalent to change and relative change is equivalent to percent change (see [Section 4.5](#)). Descriptive statistics of the LFC by MRI-PDFF results, absolute change from baseline, and relative change will be summarized by treatment group and visit.

Absolute change (and separately for relative change) from baseline in LFC will be analyzed using the same ANCOVA model presented in [Section 8.7](#). [REDACTED]

Assessments of normality will be performed as described in [Section 8.7](#).

LFC by MRI-PDFF responders will be defined as any patient with a relative decrease of at least 30% (i.e., $\leq -30\%$). Non-responders will be defined as any patient who did not have at least a 30% relative decrease (i.e., $> -30\%$). The number and percentage, with associated two-sided exact (Clopper-Pearson) 90% and 95% CIs, of patients in each category (response, nonresponse) will be presented by treatment group at [REDACTED] Week 12. A Chi-square test [REDACTED] Week 12 will be used to compare pooled TERN-101 (All TERN-101) and placebo, and each pairwise comparison between placebo and each active dose of TERN-101.

[REDACTED]

[REDACTED]

8.8.1.2. cT1

Corrected T1 (cT1) will be collected along with MRI-PDFF at sites with this capability. cT1 related to the amount of extracellular fluid present in the liver parenchyma. cT1 is derived

The cT1 metric is displayed as a median and IQR, the median will be used in all analyses.

cT1 will be analyzed in the same manner as LFC.

cT1 will be categorized as low (<800 msec), elevated (800 – 875 msec), and high (>875 msec). In addition, cT1 responders will be defined any patient with a decrease of at least 80 msec at Week 6 and 12. Non-responders will be defined any patient who did not have at least an 80 msec decrease at Week 6 and 12. For both endpoints, the number and percentage, with associated two-sided exact (Clopper-Pearson) 90 and 95% CIs, of patients in each category will be presented by treatment group at each post-baseline visit. A Chi-square test at each post-baseline visit will be used to compare pooled TERN-101 (All TERN-101) and placebo, and each pairwise comparison between placebo and each active dose of TERN-101.

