2.2.4. Treatment Assignment, Blinding, and Randomization Methodology

Patients will be randomized to TERN-101 or placebo using an Interactive Web Response System (IWRS). Approximately 96 patients will be randomized at an overall ratio of 1:1:1:1 into 4 groups receiving 5 mg (n = 24), 10 mg (n = 24), 15 mg (n = 24) TERN-101 tablet, or matching placebo (n = 24). Randomization will ensure 6 patients at each TERN-101 dose level and 6 patients in the placebo group are assigned to the PK/PD sub-study.

Investigators, patients, all study personnel, and the Sponsor will remain blinded to each patient's assigned dose group throughout the course of the study. The randomization codes will be provided to bioanalytics to allow for the exclusion of placebo patients from the PK assay.

Bioanalytics will not disclose the randomization code or the results of their measurements until the trial is officially unblinded.

Emergency unblinding procedures are outlined in Section 6.4.1 of the study protocol and in the unblinding plan.

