For log-normal data

[REDACTED] the geometric mean and geometric coefficient of variation (CV%) will also be presented. The precision of descriptive statistics will be as follows: mean, median, Q1, and Q3 to 1 more decimal place than the raw data, SD to 2 decimal places more than the raw data, the minimum and maximum to the same number of decimal places as the raw data, geometric mean to 3 significant figures, and geometric CV% to 1 decimal place.

[REDACTED]

Confidence intervals (CIs) will be provided and will be rounded to 1 decimal place, unless otherwise specified, in the table and listing shell. A full set of summary statistics will only be presented if there are 3 or more values available. If there are less than 3 values, only the min, max, and N will be presented. The other summary statistics will be denoted as not calculated (NC).

For tables where rounding is required, rounding will be done to the nearest round-off unit. For example, when rounding to the nearest integer, values \geq XX.5 will be rounded up to XX+1 (e.g., 97.5 will round up to 98), while values <XX.5 will be rounded down to XX (e.g., 97.4 will round down to 97).

All statistical tests comparing groups will be conducted at the 2-sided, 0.05 level of significance, unless otherwise specified. Summary statistics for each treatment group will be presented, as well as two-sided 90% and 95% CIs comparing groups will be provided.

Other general programming specifications are provided in [Appendix 1](#).

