7.2. Demographics and Baseline Characteristics

Demographic variables will include the following:

- Age at informed consent including the subgroup of <65 years vs ≥ 65 years
- Sex
- Race
- Ethnicity

Other baseline characteristics will include the following:

- Weight (kg)
- Height (cm)
- BMI (kg/m^2) including the following subgroup: <30, ≥ 30 - <35, ≥ 35 - <40, ≥ 40 kg/m^2
- Waist circumference (cm)
- Baseline liver stiffness by transient elastography (kPa)
- Baseline Controlled Attenuation Parameter (CAP; dB/m)
- Baseline LFC (%) by MRI-PDFF
- Baseline cTI (msec) by MRI including the following subgroup: Low (<800 msec), Elevated (800 – 875 msec), and High (>875 msec).
- Liver Biopsy within 2 years of randomization
 - Baseline fibrosis stage (F1, F2, F3)
 - Baseline NAFLD Activity Score (NAS)

- Baseline Comorbidities will be based on Medical History case report form, Medical Dictionary of Regulatory Activities (MedDRA) preferred term (PT)
 - Diabetes status (yes, no) will be defined as PT preferred term (PT) includes “diabetes mellitus” or “Diabetic neuropathy” will be assigned yes, otherwise no.
 - Hypertension (yes, no) will be defined as PT of “Hypertension” will be assigned yes, otherwise no.
 - Dyslipidemia (yes, no) will be defined as Standardized MedDRA query (SMQ) of “Dyslipidemia (SMQ)” will be assigned yes, otherwise no.
- Baseline medication use, defined as starting prior to first administration of study drug, regardless of end date:
 - Statins defined by the WHODD Standardized Drug Grouping (SDG) of “Statins”
 - Antihypertension medications defined by the WHODD SDG of “Antihypertensives”
 - Antithrombotic medications defined by WHODD SDG of “Antithrombotic drugs”
 - Antidiabetic medications defined by the WHODD SDG of “Drugs used in diabetes”
 - NASH Medications, defined as the following medications with potential beneficial effect on NASH:
 - Vitamin E defined by the WHODD drug codes beginning in “001105” or if “VITAMIN E” is found in the preferred drug name
 - Obeticholic acid defined by WHODD drug codes of 064968 01 001 through 064968 01 003
 - Pioglitazone or other PPAR γ agonists defined by WHODD ATC level 4 A10BD and A10BG
 - GLP-1 analogues defined by WHODD ATC level 4 code (term) A10BJ (Glucagon-like peptide-1 [GLP-1] analogues)
 - DPP-4 inhibitors defined by WHODD ATC level 4 code (term) A10BH (Dipeptidyl peptidase 4 [DPP-4] inhibitors)

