8. EFFICACY ANALYSES

8.1. Adjustments for Covariates

For comparison of treatment groups with respect to change and percent change from baseline, analysis of covariance (ANCOVA)

will be used. The corresponding baseline value will be used as a covariate in the model.

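### SAP 8.8.1.2 compares three ordered cT1 categories with a chi-square test that uses neither their order nor the baseline category; a baseline-stratified ordinal test is a nearly free improvement.

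*SAP*

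**What the plan says.** SAP 8.8.1.2 sets the levels: "cT1 will be categorized as low (<800 msec), elevated (800 – 875 msec), and high (>875 msec". It also defines a cT1 responder by a within-patient fall of at least 80 msec. For both, it plans counts with exact intervals and then: "A Chi-square test at each post-baseline visit will be used to compare pooled TERN-101 (All TERN-101) and placebo, and each pairwise comparison between" (the pairs being every dose against placebo). No trend test, ordinal score or stratification is stated for the three-level category.

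SAP 7.2 lists baseline cT1 "by MRI including the following subgroup: Low (<800 msec), Elevated" and High, with the same cut-points, but only for the baseline summary.

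Continuous cT1 follows the liver-fat methods, that is, the ANCOVA of SAP 8.7 on absolute and relative change. SAP 8.1 says of that model: "The corresponding baseline value will be used as a covariate in the model".

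The number of patients with cT1 is open: "Corrected T1 (cT1) will be collected along with MRI-PDFF at sites with this capability". SAP 8.6 describes all testing as nominal and exploratory, without multiplicity adjustment.

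**The concern.** Low, elevated and high are steps on one scale, and a treatment that lowers cT1 should move patients down it. A Pearson chi-square on a 2 x 3 table spends (2 − 1)(3 − 1) = 2 degrees of freedom. It gives no more weight to a consistent downward move than to patients leaving the middle level in both directions.

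The test also ignores where each patient started. If cT1 is reasonably stable within a patient, the entry category goes far towards deciding the Week 6 or Week 12 category. A chance imbalance at entry then passes straight into the post-baseline table, in either direction. Arms hold at most about 24 patients, and fewer if some sites cannot measure cT1, so such imbalances will be common.

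At stake is one exploratory comparison. It could miss a real shift, or show an apparent one that only reflects the starting mix.

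**Working it through.** **Inputs from the documents.** Test level: "All statistical tests comparing groups will be conducted at the 2-sided, 0.05 level of significance, unless otherwise specified". Sizes: "Approximately 96 patients will be randomized at an overall ratio of 1:1:1:1 into 4 groups receiving 5 mg (n = 24), 10 mg (n = 24" and so on, giving at most 24 v 24 per dose and 24 v 72 pooled. Cut-points are 800 and 875 msec. The readable text states no cT1 power, so there is no figure to reproduce.

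**Assumed, not in the documents.** Mean, SD, treatment shift, baseline-to-visit correlation, and the number of patients scanned per arm.

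**Tests compared.**
- Chi-square: Pearson, 2 df.
- Trend: 1 df, no baseline.
- Stratified mean score: scores 0/1/2 within baseline category *h*. With T_h the score sum in the treated arm, n_1h and n_2h the two arm sizes, N_h their total, and m_h and s²_h the stratum mean and variance of the scores, Q = [Σ(T_h − n_1h·m_h)]² / Σ(n_1h·n_2h·s²_h / N_h), referred to chi-square with 1 df.
- ANCOVA of continuous cT1 with baseline as covariate.

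**Cost of ignoring order alone (analytic).** At equal noncentrality, a 1-df test with power 0.50 (λ = 1.96² = 3.84) has power 0.40 on 2 df. One with power 0.80 (λ = (1.96 + 0.84)² = 7.84) has 0.71.

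**Cost of ignoring order and baseline together (simulation).** Bivariate normal cT1, mean 850, SD 100 msec, 1,500 trials per row; the Monte Carlo standard error is at most √(0.25/1500) = 0.013. Power lost = 1 − chi-square/stratified.

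| Arms | Corr. | Shift (msec) | Chi-square | Trend | Stratified | ANCOVA | Lost |
|---|---|---|---|---|---|---|---|
| 24 v 24 | 0.5 | 40 | 0.171 | 0.226 | 0.258 | 0.331 | 34% |
| 24 v 24 | 0.5 | 80 | 0.558 | 0.667 | 0.711 | 0.879 | 22% |
| 24 v 24 | 0.7 | 40 | 0.174 | 0.217 | 0.267 | 0.457 | 35% |
| 24 v 24 | 0.7 | 80 | 0.565 | 0.665 | 0.809 | 0.973 | 30% |
| 24 v 24 | 0.85 | 40 | 0.178 | 0.226 | 0.398 | 0.729 | 55% |
| 24 v 24 | 0.85 | 80 | 0.554 | 0.677 | 0.907 | 0.999 | 39% |
| 24 v 72 | 0.5 | 40 | 0.275 | 0.344 | 0.379 | 0.505 | 27% |
| 24 v 72 | 0.5 | 80 | 0.773 | 0.842 | 0.883 | 0.971 | 12% |
| 24 v 72 | 0.7 | 40 | 0.261 | 0.325 | 0.436 | 0.648 | 40% |
| 24 v 72 | 0.7 | 80 | 0.777 | 0.845 | 0.935 | 0.997 | 17% |
| 24 v 72 | 0.85 | 40 | 0.243 | 0.310 | 0.557 | 0.879 | 56% |
| 24 v 72 | 0.85 | 80 | 0.772 | 0.865 | 0.991 | 1.000 | 22% |

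The full grid also took means of 850 and 900 and sizes of 12 v 12 and 12 v 36. Across it the chi-square kept 67–102% of the stratified test's power at correlation 0, 55–88% at 0.5–0.7, and 41–78% at 0.85.

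**Second simulation.** Mean 860, SD 90, shifts of 40 and 60 msec, arms of 15 or 24, and 72 v 24 pooled. The loss was 22–43% at correlations of 0.5–0.7 and 36–57% at 0.85. The stratified test had more power in every setting, with type I error of about 4–6%.

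**Why the correlation decides the size.** Suppose change over 12 weeks is scan noise only, with between-patient SD 80–100 and repeat-scan SD 30–40. The implied correlation is 80²/(80² + 40²) = 0.80 to 100²/(100² + 30²) = 0.92. At 24 per arm and 60 msec, power is then 0.46 v 0.87 (mean 850, SDs 80/30) and 0.30 v 0.66 (mean 880, SDs 100/40), losses of 47% and 55%. Adding real variation in change of SD 60 msec brings the correlation to 0.72 and 0.75. Power becomes 0.33 v 0.53 and 0.24 v 0.45, losses of 38% and 47%.

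**Chance imbalance.** With no effect and a correlation of 0.80–0.92, in the quarter of simulated trials with the largest baseline-category imbalance, the chi-square rejected in about 9–14% and the stratified test in about 3–7%. Averaged over all trials, the chi-square's error stays near 5% (0.042–0.064 in the null settings at correlation 0.7).

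**The case against.** The case against giving this much weight is strong, and most of it stands.

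- **The information is already used.** The baseline-adjusted ANCOVA of continuous cT1 had more power than every categorical test in all settings with an effect, for example 0.973 against 0.809 and 0.565. SAP 2.3.3 lists the cT1 endpoint only as absolute and relative change; the three-level category is not in that list.
- **The 80 msec responder already uses baseline,** because it is a within-patient change. A reader might infer that every categorical cT1 comparison leaves baseline out. That is true only of the three-level one.
- **Nothing is decided by this test.** SAP 8.6 makes it nominal, and protocol 9.2 sets the sample size without regard to power.
- **The size is assumption-driven.** A reader might infer that the plan gives up about half of its available power on cT1. The documents do not support that. They give none of the quantities it needs, the figure requires a high correlation and usually a modest effect, and the pooled comparison can lose as little as 12–17% (80 msec shift, correlation 0.5–0.7).
- **Redaction.** Parts of SAP 8.8.1 and 8.8.1.1 are blacked out, so further cT1 analyses cannot be excluded.

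What survives is narrow. The test named for the three-level category is readable and unordered, it has no baseline term, and a better one needs only data already collected.

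**Conclusion.** The point holds as a low-severity improvement to one exploratory comparison. The unordered, unadjusted test is a poor match for ordered categories whose baseline version SAP 7.2 already defines.

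Under assumed values (SD about 90 msec, shift 40–60 msec, 15–24 per arm and 72 v 24 pooled), it loses roughly 20–45% of the power of the stratified ordinal test at a baseline correlation of 0.5–0.7. The loss reaches about half only if the correlation is near 0.85 or higher. Larger effects shrink it, and at correlation 0 it can vanish.

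This is not an error that invalidates a result: the chi-square's overall error rate is about right, and the cT1 assessment as a whole rests on the more powerful ANCOVA.

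**What to change.** In SAP 8.8.1.2, for the three-level category only, replace the chi-square with a Cochran-Mantel-Haenszel row-mean-score test (scores 0, 1, 2) stratified by baseline cT1 category as defined in SAP 7.2. Apply it to pooled TERN-101 v placebo and to each dose v placebo. Print the baseline-to-visit shift table beside it. Leave the 80 msec responder analysis and the continuous ANCOVA as they are.

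The cost is one SAP sentence, one procedure option and one table. Patients without a baseline cT1 drop out of this test, but they cannot enter the cT1 change analyses either. A baseline stratum with patients in only one arm adds nothing to the statistic. The choice should be made before unblinding; if made later, the clinical study report should identify it as a change, as SAP 1 requires for significant changes.

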8.8.2. Liver Function Tests

LFTs for efficacy analyses include AST, ALT, and GGT. ALT analyses are described in [Section 8.7](#)). Descriptive statistics of LFT values, change from baseline, change from end of treatment, percent change from baseline, and percent change from end of treatment will be presented by treatment group for each visit using the Efficacy Analysis Set.

Change (and separately percent change) from baseline will be analyzed using the same ANCOVA model presented in [Section 8.7](#) and the MMRM model in [Section 8.7.1](#) for each post-

baseline and follow up visit using observed data only. Change (and separately percent change) from end of treatment in LFTs will be analyzed using the same ANCOVA model presented in [Section 8.7](#).

Figures of LS mean (\pm SE) AST and GGT change from baseline and percent change from the MMRM model will be presented over time by treatment group.

Assessments of normality will be performed as described in [Section 8.7](#).

8.8.3. NASH and Fibrosis Biomarkers

Markers of hepatic fibrosis and apoptosis include CK-18 (M30 and M65), PIIINP, TIMP-1, HA, and Pro-C3. Descriptive statistics of biomarker values, change from baseline, and percent change from baseline will be presented by treatment group for each visit using the Efficacy Analysis Set.

Change (and separately percent change) from baseline will be analyzed using the same ANCOVA model presented in [Section 8.7](#). Sensitivity analyses using the PP and Treatment Completer Analysis Sets will be presented if the analysis set differs from the Efficacy Analysis Set by more than 10 patients total.

Assessments of normality will be performed as described in [Section 8.7](#).

[REDACTED]

8.8.3.1. Fibrosis-4 (FIB-4) Score

The Fibrosis-4 (FIB-4) score helps to estimate the amount of scarring in the liver. The FIB-4 score is calculated as: $[\text{Age (years)} \times \text{AST (U/L)}] \div [\text{Platelet Count (10}^9/\text{L}) \times \text{ALT (U/L)}^{0.5}]$. Age at informed consent will be used. Lab values at each visit, from the same visit, will be used. The central lab calculation of FIB-4 will be used in analyses. Programming will also calculate the score programmatically for validation. Baseline AST, Platelets, and ALT will be the mean of all available evaluations, including any unscheduled or repeat assessments, prior to the first administration of study drug, per [Section 4.7.2](#). The FIB-4 score will be calculated at baseline and at Week 6, Week 12, and Week 16.

The FIB-4 score will be analyzed in the same manner as specified in [Section 8.8.3](#).

8.8.3.2. Enhanced Liver Fibrosis (ELF) Score

The enhanced liver fibrosis (ELF) score will be calculated as: $2.278 + 0.851 \ln(\text{HA}) + 0.751 \ln(\text{PIIINP}) + 0.394 \ln(\text{TIMP-1})$. Lab values from the same visit will be used to calculate the ELF score. The central lab calculation of ELF will be used in analyses. Programming will also

calculate the score programmatically for validation. The ELF score will be calculated at baseline and post-baseline visits Week 6 and Week 12.

The ELF score will be analyzed in the same manner as specified in [Section 8.8.3](#).

8.8.3.3. Nonalcoholic Fatty Liver Disease (NAFLD) Fibrosis Score

The Nonalcoholic Fatty Liver Disease (NAFLD) fibrosis score will be calculated as: $-1.675 + 0.037 \times \text{Age (years)} + 0.094 \times \text{BMI (kg/m}^2\text{)} + 1.13 \times \text{baseline diabetes status (yes = 1, no = 0)} + 0.99 \times \text{AST/ALT ratio} - 0.013 \times \text{Platelet Count (10}^9\text{/L)} - 0.66 \times \text{Albumin (g/dL)}$. Age at informed consent and baseline diabetes status will be used. BMI at each visit will be calculated using the weight from that visit and height from screening. The baseline weight will be used for Week 2 since weight is not collected at Week 2. Lab values at each visit, from the same visit, will be used. Programming will calculate the score at each to be used in analyses. The NAFLD fibrosis score will be calculated at baseline and at Week 6, Week 12, and Week 16.

The NAFLD fibrosis score will be analyzed in the same manner as specified in [Section 8.8.3](#).

| | |
|------------|------------|
| [REDACTED] | [REDACTED] |

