5.1. Inclusion Criteria

Patients are eligible to be included in the study only if all of the following criteria apply:

1. Must be 18 to 75 years of age inclusive, at the time of signing the informed consent

3. Overweight or obese with a body mass index (BMI) ≥ 25 kg/m²

4. NASH by clinical diagnosis or biopsy as follows:

- a. For clinical diagnosis:

- i. Step 1: Liver stiffness measured by transient elastography of 7.6 - 21 kPa and controlled attenuation parameter (CAP) > 300 dB/m within 3 months prior to Screening (if results available within this timeframe, assessment does not need to be repeated at Screening).

- ii. Step 2: Patients meeting these and all other eligibility criteria will undergo MRI-PDFP and must have liver fat content $\geq 10\%$ for randomization.

- b. For biopsy diagnosis:

- i. Step 1: Fibrotic NASH (NASH CRN F1, F2, or F3) without cirrhosis diagnosed by biopsy within 2 years prior to randomization, with no subsequent treatment for NASH and stable weight ($< 5\%$ weight loss) since the time of the biopsy. Results from a previous study biopsy are permissible if drug was deemed non-therapeutic or patient received placebo.

- ii. Step 2: Patients meeting these and all other eligibility criteria will undergo MRI-PDFP and must have liver fat content $\geq 10\%$ for randomization.

5. All patients must have:

- ALT ≥ 43 IU/L for men and ≥ 28 IU/L for women
- MRI PDFP liver fat content $\geq 10\%$

6. Capable of giving signed informed consent as described in [Section 10.1.2](#), which includes compliance with the requirements and restrictions listed in the informed consent form (ICF) and in this protocol

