2.3.3. Exploratory Endpoints

- Absolute change and relative change from baseline in LFC by Magnetic Resonance Imaging (MRI) Proton Density Fat Fraction (PDFF)
- Proportion of patients achieving a $\geq 30\%$ relative decline from baseline in LFC by MRI-PDFF
- Absolute change and relative change from baseline in corrected T1 (cT1) by MRI
- Change and percent change from baseline in select liver function tests: ALT, aspartate transaminase (AST), and gamma-glutamyl transpeptidase (GGT)
- Change and percent change from baseline in plasma PD biomarkers including fibroblast growth factor-19 (FGF19), 7α -hydroxy-4-cholest-3-one (7α C4), [REDACTED]
[REDACTED]
- Change and percent change from baseline in NASH and fibrosis blood biomarkers including cytokeratin-18 (CK-18) (M30 and M65), procollagen III n-terminal propeptide (PIIINP), tissue inhibitor of metalloproteinases-1 (TIMP-1), hyaluronic acid (HA), pro-peptide of type III collagen (Pro-C3) and calculated Enhanced Liver Fibrosis (ELF), Fibrosis-4 (FIB-4) and Nonalcoholic Fatty Liver Disease (NAFLD) fibrosis scores
- [REDACTED]
[REDACTED]

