4.5. Standard Calculations

Variables requiring calculation will be derived using the following formulas:

- Days – A duration expressed in days between one date (*date1*) and another later date (*date2*) will be calculated using the following formulas:

duration in days = *date2* – *date1* + 1, where *date1* \geq first administration date

duration in days = *date2* – *date1*, where *date1* < first administration date

- Months – A duration expressed in months is calculated as the number of days divided by 30.4375
- Years – A duration expressed in years between one date (*date1*) and another date (*date2*) is calculated using the following formulas:
 - duration in years = $(date2 - date1 + 1)/365.25$, where $date1 \geq$ first administration date
 - duration in years = $(date2 - date1)/365.25$, where $date1 <$ first administration date
- Body Mass Index (BMI) – BMI is calculated using height (cm) and weight (kg) using the following formula:
$$BMI \text{ (kg/m}^2\text{)} = \text{weight (kg)} / ([\text{height (cm)} / 100]^2)$$
- Change (CHG; equivalent to absolute change for liver fat content [LFC]) – Change will be calculated as:
$$\text{Change} = \text{later value} - \text{earlier (i.e. baseline) value}$$
- Percent change (PCHG; equivalent to relative change for LFC) – Percent change will be calculated as:
$$\text{Percent change} = ([\text{Change}] / \text{earlier [i.e. baseline] value}) \times 100$$

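### The SAP plans percent change from baseline for the NAFLD fibrosis score, a score that can be zero or negative, so the sign of the result depends on the baseline

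*SAP*

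**What the plan says.** The requirement comes from four places in the SAP.

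- Section 2.3.3 lists "Change and percent change from baseline in NASH and fibrosis blood biomarkers including cytokeratin-18" and other markers. The same bullet ends with the calculated scores, including "Fibrosis-4 (FIB-4) and Nonalcoholic Fatty Liver Disease (NAFLD) fibrosis scores".
- Section 8.8.3 asks for descriptive statistics of values, change and percent change by visit. On modelling it says: "Change (and separately percent change) from baseline will be analyzed using the same ANCOVA model presented in" Section 8.7.
- Section 8.8.3.3 gives the score formula and then says: "The NAFLD fibrosis score will be analyzed in the same manner as specified in" Section 8.8.3.
- Section 4.5 defines percent change as the change divided by the earlier (baseline) value, times 100. The denominator keeps its sign, and no exception is visible for values at or below zero.

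Two general provisions might act as safeguards. Section 8.7 has a visual normality check with a Wilcoxon and Hodges-Lehmann fallback, which Section 8.8.3 adopts. Section 4.4 allows a transformation, with ln and log10 as examples.

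**The concern.** Percent change is meaningful for a quantity with a true zero that stays positive. The NAFLD fibrosis score is a linear index with an arbitrary zero. At a negative baseline a fall in the score, which is an improvement, is reported as a percent increase. At a positive baseline the same fall is reported as a percent decrease. Close to zero the ratio becomes very large in either direction.

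The means, LS means, treatment differences and confidence intervals for percent change in this listed endpoint therefore have no fixed direction. A dose that lowers the score could appear to raise it in that table while the absolute-change table shows the reverse, and the visible text has no rule for which to believe. FIB-4 is always positive, so this sign reversal does not arise for it.

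**Working it through.** **Inputs.** From SAP Section 8.8.3.3: score = -1.675 + 0.037 × age + 0.094 × BMI + 1.13 × diabetes + 0.99 × AST/ALT - 0.013 × platelets - 0.66 × albumin. From Protocol Sections 5.1 and 5.2: age 18 to 75, BMI at least 25, albumin at least 3.5 g/dL, platelets at least 150 × 10⁹/L, diabetes allowed unless HbA1c exceeds 9.5%. The plan gives no numerical result for this score, so there is no figure to reproduce.

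**Step 1: does the score cross zero among eligible patients?** AST/ALT ratios and the values away from the eligibility limits are illustrative.

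- Age 18, BMI 25, no diabetes, AST/ALT 0.5, platelets 400, albumin 5.0: -1.675 + 0.666 + 2.350 + 0 + 0.495 - 5.200 - 3.300 = -6.664.
- Age 50, BMI 35, no diabetes, AST/ALT 0.75, platelets 250, albumin 4.4: -1.675 + 1.850 + 3.290 + 0 + 0.7425 - 3.250 - 2.904 = -1.947.
- Age 60, BMI 38, diabetes, AST/ALT 0.8, platelets 220, albumin 4.3: -1.675 + 2.220 + 3.572 + 1.130 + 0.792 - 2.860 - 2.838 = +0.341.
- Age 75, BMI 45, diabetes, AST/ALT 1.2, platelets 150, albumin 3.5: -1.675 + 2.775 + 4.230 + 1.130 + 1.188 - 1.950 - 2.310 = +3.388.

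It does.

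**Step 2: apply Section 4.5 to one fixed improvement.** A platelet rise of 25 lowers the score by 25 × 0.013 = 0.325. The second and third baselines are simply values inside the range from step 1.

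| Baseline | Calculation | Percent change |
|---|---|---|
| -1.947 | -0.325 / -1.947 | +16.7% |
| -0.136 | -0.325 / -0.136 | +239% |
| +0.741 | -0.325 / +0.741 | -43.9% |

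The absolute change is -0.325 in every row.

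**Step 3: how many baselines might be negative or near zero?** The documents give limits, not distributions, so this rests on assumption. Four assumed populations, truncated at the eligibility limits, gave:

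| Assumed population | Baseline below 0 | Within 0.1 of 0 |
|---|---|---|
| Mean age 45, BMI 33, 30% diabetic | 97% | 1% |
| Mean age 50, BMI 36, 50% diabetic | 87% | 4% |
| Mean age 55, BMI 37, 60% diabetic | 74% | 6% |
| Mean age 60, BMI 39, 70% diabetic | 50% | 7% |

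Of 96 patients, about 1 to 7 would lie within 0.1 of zero.

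**Step 4: what happens to the planned ANCOVA?** Simulated trials had 24 patients per arm, an assumed SD of change of 0.35 and an assumed true improvement of 0.1, 0.2 or 0.4. The assumed populations had 61-91% of baselines negative.

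- Percent change: wrong sign in about 51-72% of trials; significant in the right direction in about 1% or fewer.
- Absolute change: significant in the right direction in about 15%, 48% and 97% of trials at 0.1, 0.2 and 0.4.

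The wrong-sign share follows the negative share. With half the baselines negative it is a coin toss, and with 97% negative it is higher than the range above.

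**Step 5: do the safeguards help?** The Wilcoxon and Hodges-Lehmann fallback limits the pull of extreme values but leaves the reversed signs in place. At a true improvement of 0.4, in four populations with 68-91% of baselines negative, the Hodges-Lehmann difference had the wrong sign in 82-99% of trials. A log transformation is undefined for negative values.

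**The case against.** The strongest reply is that little depends on this. The score is one of three calculated scores in a single exploratory bullet. SAP Section 8.6 calls all testing nominal, descriptive and exploratory. No visible decision rule uses the score, and Section 8.8.3 already plans an ANCOVA on absolute change. All of that stands, and it is why the severity is low. It does not make the percent-change output correct.

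Text next to Sections 8.8.3 and 8.8.3.3 is blacked out, so a score-specific exception cannot be excluded. Against that, the visible Section 2.3.3 names percent change for this score, and Section 4.5 shows no exception.

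A reader might infer two stronger things.

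- **That most eligible patients have a negative score.** The documents do not say so. Under the assumed populations the share runs from 50% to 97%. The sign reversal itself does not depend on that share.
- **That percent change throws away nearly all of an analysis with 97% power.** The 97% belongs to a true improvement of 0.4, for which the documents give no source. Age and diabetes status are fixed in the formula, so taken one at a time 0.4 needs a platelet rise of about 31 (0.4 / 0.013) or a BMI fall of about 4.3 (0.4 / 0.094). If ALT falls proportionally more than AST, the ratio term raises the score. At 0.2 the absolute-change analysis has about 48% power, and at 0.1 about 15%. Percent change is uninformative at every effect tried, but the contrast is much smaller at modest effects.

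**Conclusion.** The percent-change analysis of the NAFLD fibrosis score is wrong as written, at low severity. The reversal of sign and the extreme values near zero follow from two SAP formulas and the eligibility limits, with no outside figure. The wrong-sign frequency of about 51-72% rests on assumed baseline distributions, an assumed SD of change of 0.35 and assumed improvements of 0.1 to 0.4; it shows the scale and does not predict this trial. The documents do not support reading this as the loss of the endpoint, because the absolute-change analysis remains valid, or as a threat to the primary safety or secondary ALT results.

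**What to change.** In SAP Section 8.8.3.3, state that the NAFLD fibrosis score is analysed as absolute change from baseline only, and that percent change is not calculated because the score can be zero or negative. In Section 2.3.3, limit this score to change from baseline.

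The cost is two wording edits and fewer outputs to produce. No data collection or patient is affected. If the SAP is not reissued, its Section 1 allows a change to planned analyses to be documented in the clinical study report.
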